## **SPONSOR CONTACTS**

### **ACADIA Medical Contact:**

### **ACADIA Clinical Contact:**

## PROTOCOL SYNOPSIS

Protocol Number	ACP-103-032
Title	A Double-Blind, Placebo-Controlled Study to Examine the Safety and Efficacy of Pimavanserin for the Treatment of Agitation and Aggression in Alzheimer's Disease
Phase of Development	2
Name of Drug	Pimavanserin
Indication	Agitation and Aggression in Alzheimer's Disease (AD)
Sponsor	ACADIA Pharmaceuticals Inc. [REDACTED]
Sponsor Contact	[REDACTED]
Medical Monitor	[REDACTED]
Test Product, Dose, and Mode of Administration:	Pimavanserin 34 mg (provided as 2×17 mg tablets), pimavanserin 20 mg (provided as 2×10 mg tablets), or matching placebo (2×placebo tablets) will be administered orally once daily. 17 mg of the active moiety is dosed as 20 mg of the salt pimavanserin tartrate; 10 mg of the active moiety is dosed as 11.8 mg of the salt pimavanserin tartrate.
Objectives	
The purpose of this study is to evaluate the efficacy and safety of pimavanserin at doses of 34 mg and 20 mg, compared with placebo in the treatment of agitation and aggression in subjects with probable AD.
 
Primary Objective:
 

• To evaluate the efficacy of pimavanserin compared with placebo in the treatment of agitation and aggression after 12 weeks.

	
Secondary Objective:
 

• To evaluate the efficacy of pimavanserin compared with placebo on caregiver burden

 
Exploratory Objectives:
 

• To evaluate the efficacy of pimavanserin compared with placebo for the following:

– Clinician's global assessment of treatment benefit

– Other neuropsychiatric symptoms

– Functional status

– Sleep and daytime wakefulness

– Cognition

– Need for rescue medication

• To evaluate the safety and tolerability of pimavanserin

• To evaluate the plasma concentrations of pimavanserin and the major metabolite AC-279

Methodology	
This study will be conducted as a Phase 2, 12-week, randomized, double-blind, placebo-controlled, multicenter, outpatient study designed to assess the safety and efficacy of pimavanserin at doses of 34 mg and 20 mg versus placebo in subjects with a diagnosis of probable AD according to the National Institute on Aging-Alzheimer's Association (NIA-AA) guidelines who have clinically significant agitation/aggression and who meet the following criteria:
 

• Mini-Mental State Examination (MMSE) score of 5 to 26 (inclusive) at the Screening Visit

• Neuropsychiatric Inventory-Clinician Rating Scale (NPI-C) combined agitation and aggression domain score of <math>\geq 14</math> at both the Screening and Baseline visits

 
Screening Period
 
The screening period will be at least 2 to 4 weeks in duration. Subjects will have psychosocial therapy for the duration of the screening period prior to randomization. Subjects on antipsychotic medication at the beginning of the screening period will discontinue that medication (wash-out of at least 5 half-lives) during the screening period. Subjects who screen fail will be allowed to rescreen with agreement of the Medical Monitor.
 
Double-Blind Treatment Period (Baseline through Week 12)
 
The Baseline visit (Day 1) may occur as soon as all screening procedures are completed and subject eligibility has been confirmed. Subjects will be randomized in a 1:1:1 ratio to 1 of 3 treatment groups (pimavanserin

	
34 mg, pimavanserin 20 mg, or placebo), and stratified according to geographic region (North America, Europe, or Rest of World). Clinic visits occurring after Baseline will be conducted at Weeks 2, 4, 8, and 12, or upon early termination (ET) from the study. It is recommended that the subject take the study drug at approximately the same time each day.
 
All concomitant medications, including cholinesterase inhibitors, memantine, antidepressants, and other permitted medications, should be expected to remain at a stable dose throughout the study.
 
Subjects who successfully complete the 12-week treatment period will be eligible to enroll in an open-label safety extension study if they qualify. For subjects who discontinue prematurely from the study or who do not enroll in the open-label extension study, a follow-up safety assessment will be conducted by telephone call approximately 30 days after the last dose of study drug.

Number of Study Sites	Approximately 70 study sites will participate in this study.
Number of Subjects Planned	The original planned sample size was approximately 432. For business reasons, not related to safety, the enrollment (randomization) of new subjects into the study was stopped after 111 subjects were randomized. The last subject was randomized into the study on November 2, 2017.
Study Population	
Subjects who meet all of the inclusion criteria and none of the exclusion criteria are eligible to enter the treatment phase.
 
Protocol waivers for eligibility will not be granted by the Sponsor under any circumstances.
 
Inclusion Criteria:
 

1. Can understand the nature of the trial and protocol requirements and provide signed informed consent and can understand and sign other forms necessary for participation in the trial (e.g., the Health Insurance Portability and Accountability Act [HIPAA] authorization form in the United States). The following requirements for consent must be met:

– from the subject, if the subject is deemed competent to provide informed consent

– from an appropriate person according to national and local regulations (e.g., the subject's legally authorized representative [LAR] with the subject's assent), if the subject is deemed not competent to provide informed consent

2. Male or female, 50 years of age or older

3. Has a diagnosis of probable AD according to NIA-AA guidelines

	

4. Meets criteria for agitation according to the International Psychogeriatric Association (IPA) guidelines (see Appendix B)

5. Has an MRI or CT scan (brain imaging) taken during or subsequent to diagnosis of probable AD, or during the screening period (prior to Baseline)

6. Has a Mini-Mental State Examination (MMSE) score of 5 to 26 (inclusive) at Screening

7. Has agitation/aggression defined as a Neuropsychiatric Inventory-Clinician rating scale (NPI-C) combined agitation and aggression domain score of <math>\geq 14</math> at both the Screening and Baseline visits

8. Lives at home or in an assisted living or care facility (but has the capacity to visit the clinic as an outpatient). Subjects must have been at their current location for at least 3 weeks prior to Screening and plan to remain at the same location for the duration of the trial.

9. Has a designated study partner/caregiver (e.g., relative, housemate, close personal friend, or professional caregiver) who is in contact with the subject at least 3 times a week on 3 separate days. The study partner/caregiver must:

– be willing and able to accompany the subject to all clinic visits,

– be capable of routinely monitoring and reporting study drug use,

– be regarded by the Investigator as sufficiently informed to report accurately on these areas of the subject's behavioral and functional status.

10. The subject's study partner/caregiver provides written agreement that they understand the study, including the role of the study partner/caregiver and will participate in the study

11. Both subject and study partner/caregiver are fluent in and able to read the local language in which study assessments are administered at the clinical site

12. Both subject and study partner/caregiver are willing and able to participate in all scheduled evaluations and complete all required tests

13. If taking antidepressants, has been on a stable dose for at least 4 weeks prior to the Baseline visit and should be expected to remain on a stable dose throughout the trial

14. If taking cholinesterase inhibitors and/or memantine, has been on a stable dose for at least 12 weeks prior to the Baseline visit and should be expected to remain on a stable dose throughout the trial

15. If female, must be of non-childbearing potential (defined as either surgically sterilized or at least 1 year postmenopausal) or must agree to use a clinically acceptable method of contraception (e.g., oral,

--	---

	
intrauterine device [IUD; diaphragm], injectable, transdermal or implantable contraception) or abstinence, for at least 1 month prior to randomization, during the study, and 1 month following completion of the study.
 
Females of childbearing potential must have a negative serum human chorionic gonadotropin (hCG) pregnancy test at Screening and a negative urine hCG pregnancy test at Baseline
 
Exclusion Criteria:
 

1. The agitation/aggression is attributable to concomitant medications, environmental conditions, substance abuse, or active medical or psychiatric condition

2. Has a current major depressive disorder episode (within 3 months) according to the Diagnostic and Statistical Manual of Mental Disorders - Fifth Edition (DSM-5) criteria

3. Treatment with an antipsychotic medication within 2 weeks of Baseline visit or 5 half-lives, whichever is longer Investigators should not withdraw a subject's prohibited medication for the purpose of enrolling them into the study unless discontinuation of the medication is deemed to be clinically appropriate (e.g., symptoms are not well-controlled or the subject cannot tolerate the current medication).

4. Has brain abnormalities seen on an MRI or CT scan (brain imaging) taken during or subsequent to diagnosis of probable AD, that can be attributed to diseases or processes other than AD, including but not limited to:

– multiple lacunar infarcts or evidence of a single prior infarct <math>>1 \text{ cm}^3</math>;

– intracranial mass lesion (including but not limited to meningioma [<math>>1 \text{ cm}^3</math> with evidence of peritumoral edema]); or

– glioma, vascular malformation, or macrohemorrhage

5. Subject or study partner/caregiver has a medical condition (e.g., hearing, vision impairments) that would impair the ability to perform the study assessments.

6. Subject requires treatment with a medication prohibited by the protocol (see Section 5.7, Appendix C, and Appendix D)

7. Subject has had a myocardial infarction within the last 6 months prior to Screening

8. Subject has a known history or symptoms of long QT syndrome

9. Subject has a QRS interval <math><120 \text{ ms}</math> and whose Fridericia's corrected QT interval (QTcF) is <math>>460 \text{ ms}</math> at Screening or at Baseline OR subject has a QRS interval <math>\geq 120 \text{ ms}</math> and QTcF is <math>>480 \text{ ms}</math> at

--	---

	
Screening or at Baseline
 
10. Has clinically significant laboratory abnormalities that, in the judgment of the Investigator or Medical Monitor, would jeopardize the safe participation of the subject in the study
 
11. Has a history of a significant psychotic disorder prior to or concomitant with the diagnosis of probable AD including, but not limited to, schizophrenia or bipolar disorder
 
12. Subject is bedridden or has any significant medical condition that is unstable and that would either:
 

- place the subject at undue risk from study drug or undergoing study procedures; or

- interfere with the interpretation of safety or efficacy evaluations performed during the course of the study

 
13. Has participated in or is participating in a clinical trial of any investigational drug, device, or intervention, and within 4 weeks (or 5 half-lives, whichever is longer) of the Baseline visit
 
14. Subject with sensitivity to pimavanserin or its excipients
 
15. Subject has previously participated in a clinical study with pimavanserin
 
16. Subject is judged by the Investigator or the Medical Monitor to be inappropriate for the study
 
17. Subject is receiving skilled nursing care for any medical condition other than dementia (skilled nursing care includes procedures that can only be administered by a registered nurse or doctor, such as [but not limited to] intravenous administration of medication, procedures related to insertion or care of suprapubic catheters, and nasopharyngeal/tracheostomy aspiration)
 
18. Has a body mass index (BMI) of <18.5
 
19. Has an abnormal vitamin B12 result at screening or within the prior 12 months prior to Visit 1 (Screening) that has not been successfully treated
 
20. Has a Global Clinician Assessment of Suicidality (GCAS) score of 3 or 4 based on Investigator's assessment of behavior within the last 3 months at Screening or since-last-visit at Baseline

Duration of Treatment	The duration of participation for individual subjects will be up to approximately 20 weeks. Each subject will participate in a 2- to 4-week screening period, a 12-week treatment period, and a 30-day safety follow-up (telephone call) for those subjects who discontinue prematurely from the study or who do not enroll in the open-label extension study. The end of the clinical trial will be when the last subject completes the last scheduled assessment (i.e., 30-day follow-up or enrolled in the extension study).

Subject Assignment	
Eligible subjects will be randomized to receive 1 of 3 treatments in a 1:1:1 ratio within each geographic region (North America, Europe, or Rest of World):
 

• Pimavanserin 34 mg

• Pimavanserin 20 mg

• Placebo

 
It is recommended that the subject take the study drug at approximately the same time each day. Study drug can be taken with or without food.

Sample Size Calculations	The original planned sample size was approximately 432. For business reasons, not related to safety, the enrollment (randomization) of new subjects into the study was stopped after 111 subjects were randomized. The last subject was randomized into the study on November 2, 2017. Thus, this study is not powered to definitively evaluate efficacy measures and only descriptive summaries will be provided.
Efficacy Assessments and Endpoints	
Primary Endpoint:
 

• Change from Baseline to Week 12 in CMAI total score

 
Secondary Endpoint:
 

• Change from Baseline to Week 12 in the ZBI total score

 
Exploratory Endpoints:
 

• Modified Alzheimer's Disease Cooperative Study – Clinical Global Impression of Change (mADCS-CGIC) agitation score

• Change from Baseline in NPI-C combined agitation and aggression domain scores

• Change from Baseline in NPI-C individual agitation and aggression domain scores

• Change from Baseline to Week 12 in Alzheimer's disease Cooperative Study – Activities of Daily Living Inventory (ADCS-ADL) score

• Change from Baseline to Week 12 in NPI-C total score

• Change from Baseline to Week 12 in NPI-C sleep disorders domain score

• Change from Baseline to Week 12 in NPI-C combined delusions and hallucinations domain scores

• Change from Baseline to Week 12 in NPI-C combined dysphoria and apathy/indifference domain scores

• Change from Baseline to Week 12 in individual NPI-C domain scores (other than agitation, aggression, and sleep disorders)

• Change from Baseline in CMAI subscale scores

	

• Change from Baseline in Karolinska Sleepiness Scale (KSS) score

• Change from Baseline in MMSE score

• Proportion of subjects taking any rescue medication during the 12-week treatment period

Safety and Tolerability Assessments and Endpoints	
Safety will be evaluated descriptively on the basis of the following assessments:
 

• Incidence and severity of treatment-emergent AEs (TEAEs), serious AEs (SAEs), and withdrawals due to adverse events (AEs)

• Global Clinician Assessment of Suicidality (GCAS)

• Clinically important changes in the following safety assessments: vital sign measurements, weight, clinical laboratory assessments, physical examinations, and electrocardiograms (ECGs)

 
An independent Safety Monitoring Committee (SMC) will review safety information per the SMC charter.

Pharmacokinetic Assessments and Endpoints	
Blood samples of pimavanserin will be collected at Baseline (pre-dose), Weeks 2, 4, and 12 (end of study [EOS]/ET). (Note: If collection at Week 2 does not occur, then collection should be attempted at Week 8.) When possible, blood samples of pimavanserin will be collected from subjects who experience an SAE or an AE leading to discontinuation.
 
For all PK samples (scheduled and unscheduled), the dates and times of administration of the last 3 doses of study drug should be recorded. For samples collected from subjects who experience an SAE or an AE leading to discontinuation, the date and time of the last dose prior to the SAE or AE should also be recorded.
 
Plasma concentration data will not be analyzed until the official unblinding of the clinical database at the end of the study.
 
Pharmacokinetic Endpoint:
 

• Plasma concentration of pimavanserin and AC-279

Statistical Methods	
The Full Analysis Set includes all randomized subjects who received at least 1 dose of blinded study drug and who have both a baseline value and at least 1 post-baseline value for the CMAI total score. The Full Analysis Set will be used for the summary of all efficacy endpoints.
 
The Per-protocol (PP) Analysis Set will be defined prior to unblinding the study for the final summaries. Subjects will be summarized based on their randomized treatment assignment.
 
Safety summaries will be conducted using the Safety Analysis Set,

which is defined as all subjects who received at least 1 dose of blinded study drug.

Subgroup Analysis
 
Selected subgroup analyses will be specified in the statistical analysis plan (SAP).
 
Descriptive Statistics
 
Continuous measurement results will be reported using the number of subjects with data values, mean, standard error of the mean, median, standard deviation, minimum, and maximum. For each categorical outcome, the number and percentage of subjects in each category will be reported.
 
Missing Data
 
Handling of missing values will be described in detail in the SAP.
 
Efficacy Analyses
 
All efficacy endpoints will be summarized by treatment group using descriptive statistics. No hypothesis testing is planned.
 
The CMAI total score will be summarized using mixed model repeated measures (MMRM). The dependent variable will be the change from baseline in the CMAI total score. The independent variables in the model will include the following: treatment group (pimavanserin 34 mg, pimavanserin 20 mg, or placebo), visit (Weeks 2, 4, 8, and 12), the treatment-by-visit interaction, the baseline CMAI total score, the Baseline-by-visit interaction, and geographic region (North America, Europe, or Rest of World).
 
The mADCS-CGIC agitation score at each timepoint will be summarized using an MMRM model with effects for treatment group (pimavanserin 34 mg, pimavanserin 20 mg, or placebo), visit (Weeks 2, 4, 8, and 12), the treatment-by-visit interaction, and geographic region (North America, Europe, or Rest of World). There is no baseline value to include in the model. In addition, the proportion of subjects with moderate or marked improvement on the mADCS-CGIC will be summarized by treatment group at each timepoint using observed cases and also with missing values imputed as non-response.
 
The change from baseline to each post-baseline timepoint in the ZBI total score, the NPI-C combined agitation and aggression domain scores, NPI-C individual agitation and aggression domain scores, CMAI subscale scores, KSS, and MMSE will be summarized using an MMRM model similar to that described above for the primary endpoint, except that the baseline value of the endpoint being summarized will be included in the model instead of the baseline CMAI total score. Also, the MMSE is not measured at Week 2.

	
The change from baseline to Week 12 in the Alzheimer's Disease Cooperative Study – Activities of Daily Living (ADCS-ADL) and NPI-C total score and individual domain scores (except the agitation and aggression domains) will be summarized using an analysis of covariance (ANCOVA) model with effects for treatment group (pimavanserin 34 mg, pimavanserin 20 mg, or placebo), baseline value of the endpoint being summarized, and geographic region (North America, Europe, or Rest of World).
 
The proportion of subjects taking any rescue medication during the treatment period will be summarized by treatment groups.
 
Safety Analyses
 
Safety results will be summarized by treatment group using descriptive statistics. Adverse events will be classified into standard terminology using the Medical Dictionary for Regulatory Activities (MedDRA). Treatment-emergent AEs, fatal TEAEs, TEAEs leading to discontinuation, TEAEs related to study drug, TEAEs by maximum severity, serious TEAEs, and serious TEAEs related to study drug will all be summarized.
 
Descriptive statistics for ECG, vital signs, and clinical laboratory parameters, including changes from baseline, will be tabulated by timepoint. Additionally, categorical analyses will be conducted on the incidence of subjects with prolonged QTc intervals and changes in QTc intervals in accordance with International Council for Harmonisation (ICH) guidelines.
 
Pharmacokinetic Analyses
 
Plasma concentration data for pimavanserin and its active metabolite (AC-279) will be listed and summarized using descriptive statistics.

Date:	20 November 2017

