#### **2.3.2.2 Safety Endpoints**

- TEAEs
- SAEs
- Withdrawals due to AEs
- Global Clinician Assessment of Suicidality (GCAS)

- Clinically important changes in other safety assessments
  - Vital signs
  - Weight
  - Clinical laboratory results (hematology, serum chemistry, urinalysis)
  - Physical examinations
  - Electrocardiograms (ECGs)

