### **6.2.2 Physical Examinations**

Physical and neurological examinations will be conducted at Screening and at the Week 12 (EOS/ET) visit. At the Investigator's discretion, examinations may include a review of body systems (urogenital exam is required only if indicated) and should include a neurological examination (e.g., level of consciousness, speech, cranial nerves [including pupil equality and reactivity], motor assessment, sensory assessment, coordination, gait, reflexes, and Romberg test).

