### **9.8.5 Physical Examinations**

The results of the physical examinations at each visit (Screening and Week 12 visit) will be tabulated by treatment group.

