The laboratory values will also be summarized in shift tables by treatment group, to determine the number and percentage of subjects with values classified as below (low), within (normal) and above (high) normal ranges at Week 4 and Week 12 visits relative to the same classification at the Baseline visit. The shifts from Baseline to overall post-Baseline minimum and overall post-Baseline maximum will also be presented. For the by-visit shift summary, the denominator is the number of subjects with non-missing values at Baseline and the given visit for the given parameter and treatment group. For the summaries of shift to the overall post-Baseline minimum or maximum, the denominator is the number of subjects with non-missing Baseline and at least 1 post-Baseline value for the given parameter and treatment group. For hemoglobin, hematocrit and uric acid, the shift summaries will be presented for each gender as well as for both genders combined.

Number and percentage of subjects with potentially clinically important (PCI) laboratory values at Week 4, Week 12 visits and overall post-Baseline will be summarized by treatment group and by Baseline status (all and within normal range) for selected parameters. PCI criteria are listed in [Table 5](#) and [Table 6](#). For the overall post-Baseline summaries, all post-Baseline values will be considered, including unscheduled and out of window values. Subjects with multiple PCI values for a given parameter will be counted only once for that parameter. For the by-visit summary, the numerator for the percentage is the number of subjects with a post-Baseline PCI laboratory value for the given parameter, visit and treatment group, and the denominator is the number of subjects with non-missing values for the given parameter, visit and treatment group. For the overall post-Baseline summary, the numerator for the percentage is the number of subjects with at least 1 post-Baseline PCI laboratory value for the given parameter and treatment group and the denominator is the number of subjects with at least 1 post-Baseline laboratory value for the given parameter and treatment group. For hemoglobin, hematocrit and uric acid, the count and percentage of subjects with PCI values will be presented for each gender as well as for both genders combined. Subjects with any PCI values will be presented in an additional listing.

Table 5 Criteria for Potentially Clinically Important Laboratory Values – Hematology and Chemistry

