14.3 Vital Signs

Vital signs are assessed at Screening, Baseline, Weeks 2, 4, 8 and 12/ET visits.

Vital signs including weight, height (only at Screening), and the derived BMI will be summarized by treatment group using descriptive statistics at Baseline and all post-Baseline visits. The change from Baseline values will also be summarized by treatment group at the post-Baseline visits.

Vital sign values will be considered PCI if they meet both the observed value criteria and the change from Baseline criteria listed in [Table 7](#). The number and percentage of subjects with post-Baseline values that are PCI will be summarized by treatment group at each post-Baseline visit and for overall post-Baseline. For the overall post-Baseline summaries, all post-Baseline values will be considered, including unscheduled and out of window values. Subjects with multiple PCI values for a given parameter will be counted only once for that parameter. For the by-visit summary, the numerator for the percentage is the number of subjects with a post-Baseline PCI vital sign for the given parameter, visit and treatment group and the denominator is the number of subjects with non-missing values for the given parameter, visit and treatment group. For the overall post-Baseline summary, the numerator for the percentage is the number of subjects with at least 1 post-Baseline PCI vital sign for a given parameter and treatment group and the denominator is the number of subjects at least 1 post-Baseline vital sign for the given parameter and treatment group. Subjects with any PCI values will be presented in an additional listing.

Table 7 Criteria for Potentially Clinically Important Vital Signs

Vital Sign Parameter	Unit	Criteria ^a		
		Observed Value	And/Or	Change Relative to Baseline
Systolic blood pressure	mmHg	≥180	And	Increase of ≥20
		≤90	And	Decrease of ≥20
Diastolic blood pressure	mmHg	≥105	And	Increase of ≥15
		≤50	And	Decrease of ≥15
Pulse	bpm	≥120	And	Increase of ≥15
		≤50	And	Decrease of ≥15
Weight	kg	Not Applicable		Increase of ≥7%
				Decrease of ≥7%

^a A post-Baseline value is considered as a PCI value if it meets both criteria for observed value and change from Baseline.

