14.5 Physical Examination

Physical examination is performed at Screening and Week 12/ET visits.

Physical examination results (normal, abnormal, and not done) at Screening and Week 12 will be summarized in a frequency table by treatment group, body system and visit.

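### Clinically important change in physical examinations is a named safety endpoint, but no planned physical-examination table shows how many subjects became newly abnormal

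*Protocol*

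**What the plan says.** **Endpoint.** The Protocol Synopsis lists "Clinically important changes in the following safety assessments: vital sign measurements, weight, clinical laboratory assessments, physical examinations, and electrocardiograms (ECGs". Protocol 2.3.2.2 repeats it under "Clinically important changes in other safety assessments", with physical examinations as one of five sub-items.

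**Schedule.** Protocol 6.2.2: "Physical and neurological examinations will be conducted at Screening and at the Week 12 (EOS/ET) visit".

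**Analysis.** Protocol 9.8.5: "The results of the physical examinations at each visit (Screening and Week 12 visit) will be tabulated by treatment group". SAP 14.5 carries this out: results classed as normal, abnormal or not done "at Screening and Week 12 will be summarized in a frequency table by treatment group, body system and visit". Neither document describes a table that links a subject's Week 12 result to the Screening result, and neither defines a clinically important examination change.

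**Neighbouring assessments.** SAP 14.2: "The laboratory values will also be summarized in shift tables by treatment group". SAP 14.3: "Vital sign values will be considered PCI if they meet both the observed value criteria and the change from Baseline criteria".

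**The concern.** The endpoint is a change within a subject. The planned summary is two separate sets of counts, one per visit. Similar percentages at the two visits can mean that nobody changed, or that new abnormalities were offset by resolved ones or by the departure of subjects who were abnormal at Screening. The table cannot separate these cases.

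The examination should include a neurological part (Protocol 6.2.2 gives motor assessment, coordination and gait among its examples). The protocol background lists parkinsonism and gait disturbances among antipsychotic harms, and the study rationale is to avoid many antipsychotic adverse effects. Efficacy in this trial is descriptive only, so the safety description is a main use of the data. A count of newly abnormal subjects by arm is the natural summary of this item, and it is missing.

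**Working it through.** The documents state no figure on this point, so there is nothing to reproduce. The check has three steps.

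**1. What each assessment in the endpoint receives**

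| Assessment | Planned summary of change |
|---|---|
| Laboratory tests | Shift tables from Baseline, plus criteria for potentially clinically important values (SAP 14.2, Tables 5 and 6) |
| Vital signs | Change from Baseline, plus criteria that require both a level and a change (SAP 14.3, Table 7) |
| Weight | Increase or decrease of 7% or more (Protocol 9.8.3; SAP Table 7) |
| ECG | Change from Baseline, QTcF change categories, and limits (SAP 14.4, Table 8) |
| Physical examination | None; counts per visit only (Protocol 9.8.5; SAP 14.5) |

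**2. What counts per visit can identify**

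Let n subjects be examined at both visits, with a abnormal at Screening and b abnormal at Week 12. Let x be the number newly abnormal and r the number resolved. Then b = a − r + x, so x = b − a + r. Since r is not tabulated, x is known only to lie between max(0, b − a) and min(b, n − a).

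For illustration, take n = 111/3 = 37 per arm. The abnormal counts are assumptions, because the documents give none.

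| a | b | Range of x |
|---|---|---|
| 0 | 5 | 5 exactly |
| 5 | 5 | 0 to 5 |
| 5 | 10 | 5 to 10 |
| 10 | 5 | 0 to 5 |
| 10 | 10 | 0 to 10 |
| 15 | 15 | 0 to 15 |

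The count is exact only in special cases, such as no abnormality at Screening.

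With dropout, let 37 be examined at Screening (10 abnormal) and assume 31 at Week 12 (10 abnormal). That is 10/37 = 27%, then 10/31 = 32%. The 6 subjects who left may include 0 to 6 of those abnormal at Screening, so between 4 and 10 of the 31 were abnormal at Screening.

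- If it was 10, x can be as low as max(0, 10 − 10) = 0.
- If it was 4, x is at least 10 − 4 = 6, even with no resolution, and at most min(10, 31 − 4) = 10.

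The range is again 0 to 10. It is the same if 28 are assumed to return.

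**3. Early-termination examinations**

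SAP 5.3 assigns safety assessments to study-day windows: Week 2 is Days 2 to 21, Week 4 is Days 22 to 42, Week 8 is Days 43 to 70, and Week 12 is Days 71 to 99. SAP 5.3.1 brings early-termination visits under the same rule. An early-termination examination on Day 30 therefore maps to Week 4, and one on Day 60 to Week 8. SAP 14.5 tabulates neither week. If the window rule governs this table, subjects who left before Day 71 were examined but appear in no post-baseline column.

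**The case against.** The strongest reply is that clinically important new findings already have a planned route. Protocol 7.2 counts an unfavourable, unintended sign as an adverse event and exempts pre-existing chronic conditions only if they do not worsen. SAP 14.1 tabulates treatment-emergent events by system organ class, preferred term and severity. SAP 5 says that all data will be listed. This stands. A reader might infer that new abnormalities appear in no planned table at all, and the documents do not support that. What remains is narrower. The adverse-event tables do not show which events were examination findings, they omit abnormal results not reported as events, and a listing is not a summary by arm.

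Four further points stand in whole or in part.

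- A reader might infer that the SAP departs from the protocol. It does not. Protocol 9.8.5 plans the same tabulation, and SAP 19 correctly reports no changes. The mismatch is between endpoint and analysis, in both documents.
- A reader might infer that this examination is the only structured look at motor effects. Protocol 6.2.2 leaves part of the content to the Investigator and describes no scored motor instrument. Adverse events are assessed at every visit, and the NPI-C has an aberrant motor disturbance domain. The protocol also says that pimavanserin has no appreciable dopaminergic activity.
- The arms are randomized, so abnormality at Week 12 can be compared between arms, subject to dropout. That comparison still does not give the number newly abnormal.
- Table specifications are in a separate document (SAP 1). A shift layout there cannot be excluded, but neither document mentions one.

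**Conclusion.** The point holds in limited form. Of the five assessments in the endpoint, the physical examination alone has no summary of change, and the planned counts leave the newly abnormal number undetermined except in special cases.

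Its weight is modest. The item is one part of an exploratory-level safety endpoint, in a trial stopped at 111 subjects with descriptive summaries only, and the by-arm summary of examination change is all that is missing. The ranges in the working are what the arithmetic allows, not expected sizes. For complete data with 10 abnormal at both visits, the upper end of 10 requires all 10 subjects abnormal at Screening to resolve. The true number cannot be estimated from the documents. The early-termination point is conditional on the SAP 5.3 windows applying to SAP 14.5, which the SAP does not say separately.

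**What to change.** Add to SAP 14.5 a shift table by treatment group and body system, from Screening (normal, abnormal) to the last post-baseline examination (normal, abnormal), with early-termination examinations included whatever their study day. Report the number and percentage of subjects normal at Screening and abnormal at the last examination, among those examined at both times. Keep the existing frequency table, and record the addition in SAP 19, since Protocol 9.8.5 does not plan it.

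State the limits beside the table. A normal-to-abnormal shift does not show worsening in subjects already abnormal at Screening and carries no judgement of clinical importance, so both rest on adverse-event reporting. Screening is also 2 to 4 weeks before the first dose, so the shift should be read against placebo.

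The cost is one additional table. The data are already collected, and a shift layout is already planned for laboratory values.
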